5.8.3 Overall Response to Treatment

A comparative analysis of the response rate to the transplant between the two conditioning regimen will also be performed using the incident (CR, PR, SD) as the overall response. In addition the CR rate between the treatment arms will also be analyzed. The comparison of the response rate to the transplant with respect to the overall and CR component be performed using Mantel-Haenszel Test stratified on relapse risk status.

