3.2 Patient Inclusion and Exclusion Criteria

3.2.1 Patient Inclusion Criteria

- 3.2.1.1 Diagnosis of acute myelogenous leukemia, chronic myelogenous leukemia, other myeloproliferative disorder, or myelodysplastic syndrome
- 3.2.1.2 Any stage of disease will be considered for transplantation
- 3.2.1.3 Have a suitable related or unrelated donor (Section 3.3)
- 3.2.1.4 Age ≥ 18 but <70 yrs
- 3.2.1.5 KPS of $\geq 70\%$
- 3.2.1.6 Recovery from all hematologic and non-hematology toxicities from previous therapies.

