5.2 Secondary Endpoints

Secondary endpoints will include:

5.2.1 Overall survival (OS): Defined as time from the first dose of administration to death from any cause.

5.2.2 Overall response rates: Defined as the composite endpoint of response to treatment which includes Complete Response (CR), Partial Response (PR), stable disease (SD) as defined in International Response Criteria. We will also analyze Complete Response rate.

5.2.3 Univariate analysis of the risk of progression/relapse and mortality: In addition, multivariate analysis of the risk of progression/relapse and overall mortality will be conducted to assess influence of variables measured after the start of treatment.

5.2.4 Regimen-related toxicity: Graded and presented in a descriptive nature.

Descriptive analysis of baseline characteristics and demographics in this two-treatment arms study will be performed in the following manner. Continuous measurements will be summarized as mean (SD) or median (inter-quartile range) based on whether or not the data come from a normal distribution as validated by Shapiro-Wilks test of normality. Categorical measurements will be summarized as frequency (percentage). Proportion of overall survival will be estimated by the Kaplan-Meier product limit method. The univariate probability of the relapse and treatment-related mortality (TRM) will be calculated using cumulative incidence function.

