5.3 Accrual, Registration and Follow-up

The targeted sample size is 54 subjects. It is estimated that four years of accrual will be necessary to enroll this number of subjects. About 50 patients (49-52) underwent allogeneic transplantation at this center, indicating that an appropriate number of subjects will be available to complete this study in the time frame anticipated. Subjects will enroll uniformly over the accrual period. The randomization will be stratified by relapse risk status (high versus low). Low relapse will include: AML CR1 and CML chronic phase. All other AML, MPD and MDS patients will be considered high relapse risk. An AML CR1 patient with a history of MDS will be considered high relapse risk. All patients who are Flt3/ITD positive at any time will be considered high relapse risk. Upon establishing eligibility, subjects will be randomized in equal numbers to the FluBu and FluBuTBI arms using permuted blocks within strata.

All subjects will be followed for one year from time of transplantation, during which they will be monitored for the effects of treatment through regular clinic visits. Additional follow-up data beyond one year of progression-free survival will be obtained from HUMC Cancer Center Database.

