5.8 Secondary Endpoints

5.8.1 Secondary endpoints will include:

5.8.1.1 Overall response rates: Defined as the composite endpoint of response to treatment which includes Complete Response (CR), Partial Response (PR), stable disease (SD) as defined in International Response Criteria. We will also analyze Complete Response rate.

5.8.1.2 Overall survival (OS): Defined as time from the first dose of administration to death from any cause.

5.8.1.3 Univariate analysis of the risk of progression/relapse and mortality: In addition, multivariate analysis of the risk of progression/relapse and overall mortality will be conducted to assess influence of variables measured after the start of treatment.

5.8.1.4 Regimen-related toxicity: Graded and presented in a descriptive nature.

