5.8.5 Association of Prognostic Factors and Risk of Progression/Relapse and Mortality

A comparative analysis of risk outcomes relapse/progression, TRM, and overall Mortality will be conducted while adjusting for imbalance in other risk factors using a Cox proportional hazards model (1). To fit the multivariate model, a stepwise backward selection procedure will be used while considering the type of conditioning regimen (FluBuTBI versus FluBu), relapse risk status (low risk, high risk), age at transplant and Karnofsky performance score (<90 versus ≥ 90), donor-gender, CMV, HLA match grade, and stem cell source as potential covariates. Covariates yielding a p-value of 0.05 or less will be an indication of statistical significance. Graft-versus host disease (GVHD) will be entered as a time-dependent covariate. Both acute GVHD and chronic GVHD will be considered as subtypes of GVHD. An examination of the goodness-of-fit will be performed using Grambsch-Therneau and Martingale residual plots (2) and lowess smooth of Cleveland (3). The proportionality assumption for Cox regression will be validated by introducing a time-dependent covariate for each risk factor and outcome. Since BM blast cell count, presence of peripheral blood blast, and whether or not the patient is in CR at transplant are collinear only one variable will be used in single model fitting attempt. Thus, three different models will be considered when examining the association risk factors and disease relapse and OS. The results of this analysis will be presented in terms of relative risks (RR) along with the corresponding p values for each covariate.

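### Overall response counts stable disease as response, and both response comparisons include patients already in complete remission at transplant, so neither cleanly measures response to the regimen (minor)

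*Combined protocol and SAP*

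**What the plan says.** Sections 5.2.2 and 5.8.1.1 list overall response as a secondary endpoint composed of "Complete Response (CR), Partial Response (PR), stable disease (SD) as defined in International Response Criteria". Section 5.8.3 repeats the composite, "using the incident (CR, PR, SD) as the overall response", and adds a second comparison: "In addition the CR rate between the treatment arms will also be analyzed". Both are tested "using Mantel-Haenszel Test stratified on relapse risk status". For this test the section states no sidedness, significance level, assessment time or restriction by disease status at entry.

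Patients in remission and patients with active disease both enter. Section 3.2.1 says "Any stage of disease will be considered for transplantation". Section 5.3 defines the low-risk stratum by "Low relapse will include: AML CR1 and CML chronic phase" and puts the other patients in the high-risk stratum, including first-remission AML with prior MDS and anyone ever Flt3/ITD positive. Section 5.8.5 expects a mix, since it lists "whether or not the patient is in CR at transplant" as a candidate variable for the Cox models. No section says how a patient already in CR is scored for response.

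The marrow data exist in any case. Section 3.4.8 requires a pre-transplant marrow, and section 3.8.1 schedules restaging marrows at day 84 and at one year.

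**The concern.** A response rate for a conditioning regimen should show how often the regimen clears or reduces disease that was present. Two features of the definition work against that.

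- **Stable disease as response.** Leukemia or MDS that persists unchanged after conditioning and an allograft counts as success in the composite. Only progression, or possibly death, counts as failure.
- **Remission at entry.** A patient in CR has no disease to respond. That patient contributes kept remission, while a patient with active disease contributes achieved remission. The two are added together, and the first largely repeats the relapse endpoint.

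At stake is the reading of a formally tested secondary endpoint. Two similar, inflated rates could be taken as equal activity of the regimens when much of each rate reflects who entered in remission or whose disease merely did not progress.

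**Working it through.** **1. The plan's own figures.** The plan gives no expected response rate, CR rate or power for these comparisons. Its only power figure, 80.06% with 52 patients in section 5.4, belongs to the primary log-rank test. That figure reproduces approximately. The hazard ratio is ln(0.864)/ln(0.66) = 0.352. Uniform 4-year accrual, 1 further year of follow-up and 10% annual dropout give 52 × 0.447 = 23.3 events. Power is Φ(√(23.3/4) × |ln 0.352| − 1.645) ≈ 81%. It says nothing about response, but it confirms how the 34% and 13.6% relapse rates are meant.

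**2. Which feature touches which comparison.**

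| Feature | CR + PR + SD | CR rate |
|---|---|---|
| SD counted as response | affected | not affected |
| Patients in CR at entry | affected | affected |

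Stratifying by relapse risk does not remove the second feature. The high-risk stratum holds first-remission AML with prior MDS, Flt3/ITD-positive AML in remission and AML in later remission, together with active disease. The low-risk stratum combines first-remission AML with chronic-phase CML.

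**3. What the composite would show on the protocol's relapse rates.** Suppose progression is the only non-response. CR + PR + SD is then freedom from progression.

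- At 1 year: 1 − 0.34 = 66% vs 1 − 0.136 = 86.4%.
- At day 84 with a constant hazard: 0.66^(84/365) = 0.909 vs 0.864^(84/365) = 0.967, about 91% vs 97%.

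Power for two proportions with n per arm, one-sided 5% (assumed here, to match the plan's other tests), unstratified, where p̄ is the mean of the two rates:

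Φ{[d − 1.645·√(2p̄(1−p̄)/n)] / √([pA(1−pA) + pB(1−pB)]/n)}

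With n = 27 this gives 55% at 1 year (Fisher's exact test 44%) and 22% at day 84 (Fisher 4%). The approximation is rough near 100%, so the exact values matter at day 84.

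**4. Dilution of the composite.** Let f be the share in CR at entry and r the true CR/PR rate in active disease. Illustrative assumptions: r = 60% vs 80%, and everyone who enters in CR keeps it. The observed rate is f + (1 − f)r. The last column counts half of the remaining non-responders as SD.

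| f | CR + PR, all patients | CR + PR + SD |
|---|---|---|
| 0.5 | 80% vs 90% | 90% vs 95% |
| 0.3 | 72% vs 86% | 86% vs 93% |

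A 20-point difference in active disease becomes 10 and then 5 points at f = 0.5, or 14 and then 7 points at f = 0.3.

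**5. Dilution of the CR rate.** Illustrative assumptions: 95% of patients in CR at entry keep it, and 50% vs 80% of the others convert. The rate is 0.95f + (1 − f)r.

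| f | CR rate | Power, 27 per arm |
|---|---|---|
| 0 | 50% vs 80% | 76% |
| 0.25 | 61% vs 84% | 59% |
| 0.5 | 73% vs 88% | 39% |
| 0.75 | 84% vs 91% | 21% |
| 0.9 | 91% vs 94% | 11% |

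**6. What restriction does to power.** At f = 0.5 in step 4, all 27 per arm at 80% vs 90% gives (0.10 − 1.645 × 0.0972)/0.0962 = −0.62, a power of 27%. Restricting to 13 or 14 per arm at 60% vs 80% gives 29% or 31%. Counting SD lowers the all-patient figure to 17% (90% vs 95%).

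**The case against.** A reader might infer that both comparisons are near ceiling in each arm and cannot show a difference between regimens. The documents do not support that. They give no response rate, share in CR or assessment time. At 1 year the protocol's own relapse rates are well short of ceiling, and only a day 84 reading comes close. Deaths would lower the rates further if counted as non-response, which the plan does not address. Applying the 10% non-relapse mortality that section 5.10 assumes for FluBu to both arms, day 84 becomes 0.90 × 0.909 = 82% vs 0.90 × 0.967 = 87%.

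Other points for the plan also stand:

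- The separate CR comparison already excludes SD.
- The composite is openly defined in three places and can be read as disease control under another name.
- A stratum with little outcome variation carries little weight in a Mantel-Haenszel test, so the planned analysis may suffer less dilution than the pooled formula suggests.
- Restricting the denominator gains almost no power; the small sample is the main limit.
- How the cited response criteria classify a patient already in CR cannot be checked from these documents.
- Response is not among the objectives in sections 2.1 and 2.2. Relapse, survival and death-inclusive event-free survival are tested separately.

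These points limit severity and rule out the ceiling claim. They do not make unchanged active disease a response, and they do not supply the missing rule for patients in CR at entry.

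**Conclusion.** The definition is a real but minor weakness. Followed as written, it scores unchanged active disease as response in the composite and mixes kept with achieved remission in both comparisons. Both are diluted as measures of response to the regimen.

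The amount of dilution is unknown. On the illustrative rates, a 20-point effect in active disease shrinks to between 5 and 14 points, depending on the share in CR at entry and whether SD counts. Those figures rest on assumed response and retention rates. The day 84 figures rest on a constant relapse hazard and on ignoring deaths. Whether the composite approaches ceiling depends on an assessment time that the plan does not set. Severity is minor, because response is a secondary endpoint that drives no decision or stopping rule.

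**What to change.** In sections 5.2.2, 5.8.1.1 and 5.8.3:

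- Define overall response as CR + PR and report SD as a separate category.
- Make the overall-response and CR comparisons in patients not in CR on the pre-transplant marrow required by section 3.4.8.
- Read response at the day 84 marrow scheduled in section 3.8.1, and state how a death before that marrow is counted.
- State that patients in CR at transplant are covered by the relapse endpoint.

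The change is to wording only and needs no new procedures or patients. It costs a smaller denominator and lower reported rates. It should be presented as making the estimate interpretable, since power stays low either way.

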5.8.4 Event-Free Survival

The event is death from any cause or relapse/disease progression. The time to this event is the time from randomization to death, relapse or disease progression, loss to follow-up or the end of the study, whichever comes first. Patients alive at the time of last observation are considered censored. The Kaplan-Meier estimate of survival will be estimated separately for each treatment-group and risk status. A one-sided log-rank test stratified on risk status will be conducted at the 5% level of significance, analogous to the analysis of relapse risk described above.

5.8.5 Association of Prognostic Factors and Risk of Progression/Relapse and Mortality

A comparative analysis of risk outcomes relapse/progression, TRM, and overall Mortality will be conducted while adjusting for imbalance in other risk factors using a Cox proportional hazards model (1). To fit the multivariate model, a stepwise backward selection procedure will be used while considering the type of conditioning regimen (FluBuTBI versus FluBu), relapse risk status (low risk, high risk), age at transplant and Karnofsky performance score (<90 versus ≥ 90), donor-gender, CMV, HLA match grade, and stem cell source as potential covariates. Covariates yielding a p-value of 0.05 or less will be an indication of statistical significance. Graft-versus host disease (GVHD) will be entered as a time-dependent covariate. Both acute GVHD and chronic GVHD will be considered as subtypes of GVHD. An examination of the goodness-of-fit will be performed using Grambsch-Therneau and Martingale residual plots (2) and lowess smooth of Cleveland (3). The proportionality assumption for Cox regression will be validated by introducing a time-dependent covariate for each risk factor and outcome. Since BM blast cell count, presence of peripheral blood blast, and whether or not the patient is in CR at transplant are collinear only one variable will be used in single model fitting attempt. Thus, three different models will be considered when examining the association risk factors and disease relapse and OS. The results of this analysis will be presented in terms of relative risks (RR) along with the corresponding p values for each covariate.

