5.6 Statistical Hypothesis

The null hypothesis is that the 1 year relapse rate is 34%. It is the goal of this study to show that when fludarabine, busulfan and total body irradiation is used as the regimen the risk of relapse is 40% that of the fludarabine and busulfan regimen. Then, we are seeking a relapse rate of 13.6 % in the in the FluBuTBI regimen arm which is less than that in FluBu regimen arm. Thus, we will evaluate the hypotheses

$$H_0: \theta_A \leq \theta_B$$

$$H_A: \theta_A > \theta_B$$

where θ_A = rate of relapse in Arm A (FluBu) which is assumed to be 0.34,

θ_B = rate of relapse in Arm B (FluBuTBI).

Due to the lack of homogeneity in the outcome as a result of risk status (low versus high), it will be useful to stratified on risk status. Thus, a one-sided log-rank test stratified on risk status will be conducted to ascertain if FluBuTBI reduces the relapse rate from that in over FluBu using a 5% level of significance.

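### Section 5.8.5 lets backward selection delete the regimen term from the adjusted arm comparison, and a regimen estimate that survives is exaggerated by the significance filter

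*Combined protocol and SAP*

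**What the plan says.** Section 5.8.5 describes an arm comparison on relapse or progression, TRM and death from any cause that "will be conducted while adjusting for imbalance in other risk factors using a Cox proportional hazards model". To build that model, "a stepwise backward selection procedure will be used while considering the type of conditioning regimen". The list goes on to relapse risk status, age and Karnofsky score, and ends with "donor-gender, CMV, HLA match grade, and stem cell source as potential covariates". That makes eight named candidates, two of which are the randomized treatment and the stratification factor of section 5.3. No sentence holds either in the model.

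Further terms come on top:

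- GVHD enters as a time-dependent covariate, and "Both acute GVHD and chronic GVHD will be considered as subtypes of GVHD", so one or two terms.
- Three disease-status measures "are collinear only one variable will be used in single model fitting attempt", so one term in each of three models.

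The only p-value criterion is that "Covariates yielding a p-value of 0.05 or less will be an indication of statistical significance". The section does not call this the level for staying in the model, and it does not say whether the test is one- or two-sided. Results are to be given as relative risks with p-values; confidence intervals are not mentioned.

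**The concern.** An adjusted treatment comparison needs the treatment in the model. Under backward selection with regimen as an ordinary candidate, a regimen term that misses the stay level disappears, and the adjusted comparison then has no result for that outcome. If regimen does stay, it is because its estimate was large enough to pass the level, so the reported value is biased away from no effect.

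The same applies to relapse risk status, although section 5.6 stratifies the primary test on it because outcome is expected to differ by risk. At stake is the only covariate-adjusted regimen effect that the plan specifies. It could be missing, or be larger than the truth and published beside the primary result.

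**Working it through.** **Inputs.** Section 5.4: 1-year relapse 34% and 13.6%, one-sided 5% level, 4 years of accrual plus 1 year, 10% dropout, 26 per arm required, 27 per arm planned, stated power 80.06%. Section 5.3: each subject followed for one year, with later data from the center database. Section 5.7: analysis one year after accrual is completed.

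**1. Hazard ratio.** With exponential times, the hazards are −ln(0.66) = 0.4155 and −ln(0.864) = 0.1462 per year. HR = 0.1462/0.4155 = 0.352.

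**2. The plan's own power.** Take uniform accrual over 4 years, 1 further year, and a dropout hazard of −ln(0.9) = 0.105 per year. The chance of an observed relapse is then 0.599 (FluBu) and 0.296 (FluBuTBI). Events = 26 × (0.599 + 0.296) = 23.3. Schoenfeld power = Φ(√23.3/2 × 1.044 − 1.645) = Φ(0.876) = 80.9%, close to the stated 80.06%. The power calculation therefore implies about 23 relapses.

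**3. Two event counts.** Within one year of transplant: 27 × (0.34 + 0.136) = 12.9 with no loss, or 12.2 with exponential dropout. With follow-up to one year after accrual ends: 27 × (0.599 + 0.296) = 24.2, so about 23–24. Non-relapse deaths would lower both.

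**4. Why survivors are exaggerated.** Roughly, SE(ln HR) = 2/√events. To reach two-sided p ≤ 0.05, the estimate must satisfy |ln HR| ≥ 1.96 × 2/√events:

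- 12 events: 1.96 × 0.577 = 1.13, so HR must be below about 0.32. That is already more extreme than the true 0.352.
- 23 events: 1.96 × 0.417 = 0.82, so HR must be below about 0.44.

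**5. Simulation at true HR 0.352, 54 patients, two-sided Wald p-values.** Setting A: 15% per year non-relapse death, 70% high risk, nine baseline candidates (1,500 trials, and a repeat of 800). Setting B: 10% dropout, no competing deaths, about two thirds high risk, time-dependent GVHD, 9 or 11 terms (1,000 trials each). Both use HR 2 for high risk and null effects for the remaining covariates. A further run with about 12.6 and 23 events is included in the ranges.

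| Result | About 12 relapses | About 22–23 relapses |
|---|---|---|
| Regimen deleted, stay level 0.05 | 64–72% | 33–40% |
| Median HR when kept | 0.16–0.18 | 0.25–0.26 |
| Kept estimates more extreme than 0.352 (B) | 98–99% | 82–83% |
| Regimen deleted, stay level 0.10 to 0.20 (A, repeat) | 56% to 43% | 27% to 17% |
| Fixed model (regimen, risk): p > 0.05 | 65–73% | 32–38% |
| Fixed model: median HR when p ≤ 0.05 | 0.18 | 0.28 |
| Fixed model: median HR, all trials | 0.33–0.34 | 0.35 |
| Full model fails or diverges (B) | 19–35% | about 1% |
| A pure-noise covariate is kept (B) | 27–29% | 35–44% |
| Fixed model fails or diverges | 7–12% | under 1% (B) |

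**6. Attribution.** The fair comparison is row 2 against row 6, because both look only at trials that passed p ≤ 0.05. They nearly agree (about 0.17 against 0.18; 0.26 against 0.28), as do rows 1 and 5. With no true effect, setting B kept regimen in only 5–7% of trials, near the nominal level. The loss and the exaggeration therefore come from filtering regimen on significance at low power. The long list of terms shows up in the failure and noise rows.

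**The case against.** The strongest reply is that little hangs on this model. The section's title concerns prognostic factors. Sections 5.2.3 and 5.8.1.3 describe the multivariate work as looking at variables measured after treatment starts. The arms are compared elsewhere by stratified tests: relapse (5.7), OS (5.8.2), response (5.8.3) and EFS (5.8.4). All of that stands, and it limits the point to a secondary analysis. It does not remove it, because 5.8.5 itself promises an adjusted comparison and then makes the compared term removable.

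Other parts of the reply also stand:

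- A reader might infer that screening 9 to 11 terms causes the exaggeration. Step 6 does not support that.
- A reader might take about 12 relapses as the planned number. The one-year window gives that, but the stated power and the analysis date point to about 23.
- The 0.05 stay level is an inference, and the deletion rate depends on it. A one-sided 0.05 level in the favourable direction corresponds to the two-sided 0.10 row.
- GVHD is to be entered, which reads as included rather than screened.
- The plan does not say that selected p-values will be presented as if the model had been fixed in advance.
- A forced model is not trouble-free at about 12 events, as the last row of the table shows.

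**Conclusion.** The point holds as a defect in a secondary analysis. As written, 5.8.5 can delete the effect that it sets out to estimate, along with the stratification factor. At an assumed stay level of 0.05 and the plan's own effect size, deletion is more likely than not with about 12 relapses and happens in roughly a third or more of trials with about 22–23. Surviving estimates center on about 0.17 or 0.26 against a true 0.352. A looser stay level lowers the deletion rate but leaves regimen removable.

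The percentages rest on exponential hazards and on assumptions that the documents do not give: the stay level, HR 2 for high risk, the share at high risk, covariate and GVHD frequencies, and null effects for the other factors. They concern relapse only; nothing was computed for TRM or overall mortality.

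A reader might go further and conclude that the primary result is compromised. It is not: the stratified log-rank test in 5.7 does not use this model, and neither do the OS, EFS and response tests.

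**What to change.** Amend 5.8.5 as follows:

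- Take the regimen comparison out of backward selection. For each outcome, fit a Cox model stratified by relapse risk status, with regimen forced in and at most one or two baseline covariates named in advance (age, for example), kept whatever their p-values.
- Report the regimen hazard ratio with its 95% CI in every case.
- Name a Firth-penalised fit as the fallback if the model does not converge.
- Move the other prognostic factors and post-transplant GVHD to a separate table labelled exploratory, with regimen and risk status always in the model.
- State the follow-up window for the model, since it moves the expected relapses between about 12 and about 23.

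This changes wording only; no patients or data are added. The cost is that there will be no single selected prognostic model, and the regimen interval will be wide.

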The combination of fludarabine and intravenous busulfan (FluBu) has become the most commonly used conditioning regimen for allogeneic transplantation. Its safety profile has compared favorably to the previous regimens of cyclophosphamide and TBI or cyclophosphamide and busulfan (BuCy). Andersson et al. reported on 148 patients receiving fludarabine and busulfan for conditioning regimen compared to 67 patients receiving BuCy (7). The groups had comparable pretreatment characteristics, except that FluBu patients were older (46 versus 39 years, $P<0.01$), more often had unrelated donors (47.3% versus 20.9%, $P<0.003$), and had shorter median follow-up (39.7 versus 74.6 months). To account for improved supportive care and other unidentified factors that might have affected outcome (“period” effects), 78 acute myelogenous leukemia (AML) patients receiving Melphalan-Flu (MF), treated in parallel during this time (1997-2004) were used to estimate the period effect. The MF patients’ outcomes worsened during this period. Therefore, the period effect was unlikely to have explained the greatly improved outcome with FluBu. Patients transplanted with FluBu in their first complete remission (CR1) had a 3-year overall survival and event-free survival (EFS) of 78% and 74% respectively, whereas CR1 patients younger than age 41 had a 3-year EFS of 83%. These results supported replacing BuCy with FluBu. Bredeson et al. compared BuCy to FluBu by performing a retrospective matched-pair analysis comparing outcomes of adult patients treated with either regimen (8). One hundred and twenty cases (FluBu) and 215 matched controls (BuCy) were available for comparison. All FluBu patients also received antithymocyte globulin (ATG). Patients receiving FluBu had significantly less treatment related mortality (12% versus 34%) and grades II-IV acute graft-versus-host disease (15% versus 34%, $P<0.001$) compared to BuCy patients. The risk of relapse however, was higher in the FluBu patients (42% versus 20%, $P<0.001$). The risk of chronic GVHD and disease-free survival was similar in the cases and controls. In conclusion, the FluBu regimen has improved the treatment-related mortality but post-transplant relapse remains the main obstacle in the successful treatment of these patients.

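### The secondary Cox comparison in 5.8.5 adjusts for GVHD, which arises after randomization, so its regimen relative risk need not be the randomized effect

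*Combined protocol and SAP*

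**What the plan says.** Section 5.8.5 gives one Cox analysis two jobs. It opens as a treatment comparison: "A comparative analysis of risk outcomes relapse/progression, TRM, and overall Mortality will be conducted while adjusting for imbalance in other risk factors". It then sets out the model building: "a stepwise backward selection procedure will be used while considering the type of conditioning regimen (FluBuTBI versus FluBu", with relapse risk status and other baseline factors as further candidates. GVHD is added to the same model: "Graft-versus host disease (GVHD) will be entered as a time-dependent covariate", and "Both acute GVHD and chronic GVHD will be considered as subtypes of GVHD". Relative risks and p values are to be reported for each covariate.

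The section foresees three models, which differ only in which of three collinear measures of disease status at transplant they use. None is described as leaving GVHD out. Regimen is not said to be forced in, and nothing limits how its coefficient may be read.

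Sections 5.2.3 and 5.8.1.3 describe the purpose differently: the multivariate analysis is there to "assess influence of variables measured after the start of treatment". Section 3.7.2.1 places GVHD staging at the post-transplant visits, so it is recorded after randomization and after conditioning.

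**The concern.** Randomization protects a comparison of arms that adjusts for nothing, or only for baseline factors. GVHD is neither a baseline factor nor an imbalance between the arms at entry. If TBI alters the risk of GVHD, and GVHD alters relapse or death, then GVHD lies on the path from regimen to outcome. Holding it fixed takes that path out of the regimen coefficient. Coding GVHD as time-dependent avoids crediting patients with GVHD before it occurs, but it does not solve this problem.

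A second difficulty arises if some unmeasured patient or donor factor drives both GVHD and the outcome. Conditioning on GVHD then links regimen to that factor, and the regimen coefficient can move away from the truth in either direction.

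Backward selection adds to this. Regimen can be dropped, and a regimen effect that works through GVHD makes that more likely once GVHD is in the model. At stake is the adjusted regimen relative risk for relapse, TRM and mortality, which a reader of the results would naturally take as the covariate-adjusted treatment effect.

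**Working it through.** **The plan's own figure.** The plan states no figure for this model. Its power statement in 5.4 (80.06% with 26 per arm) concerns the log-rank test, and it reproduces. The hazard ratio is ln(0.864)/ln(0.66) = 0.352. Four years of uniform accrual, one further year and 10% dropout per year (an assumed reading of the dropout rate) give about 23.3 events. Schoenfeld's formula gives Φ(√(23.3/4) × 1.045 − 1.645) = 80.9%; a Lakatos-type calculation gives 79.1%. GVHD does not enter that test, so this point leaves the figure alone.

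**Illustration of the bias.** Only the 34% one-year relapse rate (5.4) comes from the documents; every GVHD input is an assumption.

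- Relapse hazard per year: −ln(1 − 0.34) = 0.416, times the direct TBI hazard ratio (HR) in the TBI arm, times the GVHD-to-relapse HR once GVHD has begun.
- GVHD onset hazard: 1 per year in the control arm, multiplied by the TBI-to-GVHD HR in the TBI arm.
- One year of follow-up, 400,000 simulated patients, Cox model fitted with and without GVHD as a time-dependent term.

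| TBI-to-GVHD HR | GVHD-to-relapse HR | Direct TBI HR | Regimen HR, no GVHD term | Regimen HR, GVHD in model |
|---|---|---|---|---|
| 1 | 0.5 | 1 | 0.99 | 0.99 |
| 1.5 | 0.5 | 1 | 0.93 | 1.00 |
| 2 | 0.5 | 1 | 0.88 | 1.00 |
| 2 | 0.3 | 1 | 0.81 | 0.99 |
| 2 | 0.5 | 0.352 | 0.31 | 0.35 |

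In the first row TBI does not affect GVHD and adjustment changes nothing (the true value is 1.00; the 0.99 is simulation error). In the other rows the adjusted model returns the direct effect and loses the part that runs through GVHD.

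**Shared unmeasured cause.** Now let TBI double the GVHD hazard but have no effect on relapse by any path, and let an unmeasured factor act on both outcomes (log-HR 0.8 per SD on relapse, and +0.8 or −0.8 on GVHD). The regimen HR without GVHD is 1.00. With GVHD in the model it is 0.90 or 1.11. The adjustment can therefore create an effect as well as remove one.

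**TRM.** Assume GVHD in 40% versus 55–60%, onset between day 20 and day 150, a GVHD-to-TRM HR of 3–4 and no direct TBI effect. A total TRM HR of roughly 1.1 to 1.2 becomes about 1.0 after adjustment.

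**Against the precision available.** Using the two non-relapse mortality figures in 5.10 as an assumed range (10% to 20%), 54 patients give 54 × 0.10 = 5.4 to 54 × 0.20 = 10.8 deaths. The standard error of the log HR is about 2/√deaths, or 0.86 to 0.61. The 95% limits then lie a factor of exp(1.96 × 0.86) = 5.4 to exp(1.96 × 0.61) = 3.3 either side of the estimate, far wider than the shifts above.

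**The case against.** The strongest reply is that this is a prognostic model. The heading of 5.8.5 speaks of association with prognostic factors, and 5.8.1.3 says "multivariate analysis of the risk of progression/relapse and overall mortality will be conducted to assess influence of variables measured after the start of treatment". A time-dependent GVHD term is a proper way to answer that question. This stands, and it is why the GVHD model should be kept. It does not cover the regimen comparison that the opening sentence of 5.8.5 assigns to the same model.

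A reader might infer that an excess of TRM acting through GVHD would be hidden from the trial. The documents do not support that. The log-rank tests for relapse (5.7), overall survival (5.8.2) and event-free survival (5.8.4) are stratified on risk status only. Section 5.2 plans cumulative incidence for TRM, 5.8.6.1 compares its incidence between arms, and 5.10 sets a stopping rule on non-relapse mortality in the TBI arm. None of these adjusts for GVHD.

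A reader might also take the acute GVHD rates of 15% versus 34% in section 1.2 as proof that TBI changes GVHD. Those figures compare FluBu with BuCy in a retrospective matched analysis in which all FluBu patients also received ATG. They are not a contrast of TBI with no TBI. In this trial both arms have the same ATG and GVHD prophylaxis (3.10.2 and 3.10.3).

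Finally, with 54 patients, shifts of the size illustrated would rarely change a conclusion. That is also fair. It limits the weight of the point, but the model is still mis-specified for a regimen comparison.

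**Conclusion.** The point holds for the secondary Cox model in 5.8.5 and for nothing else. As written, its regimen relative risk is conditional on a variable that arises after randomization, and the term itself may be dropped by selection. If TBI affects GVHD, that relative risk is not the randomized total effect.

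The size is unknown because the documents give no GVHD rates for these two regimens; it is about zero if TBI does not affect GVHD. It would be too strong to say that the model removes exactly the part of the TBI effect that acts through GVHD. That requires a correctly specified model and no unmeasured cause shared by GVHD and the outcome; otherwise the error can go either way. The simulated shifts show mechanism and direction under assumed inputs and are not estimates for this trial. The primary analysis, the survival tests and safety monitoring are unaffected.

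**What to change.** In 5.8.5, state that the regimen effect on relapse/progression, TRM and overall mortality is estimated from a Cox model with regimen and risk stratum forced in and baseline covariates only. Keep the time-dependent GVHD model as a separate analysis, labelled prognostic, and say that its regimen coefficient is not interpreted as the treatment effect. In 5.2.3 and 5.8.1.3, state that the analysis of variables arising after treatment begins refers to that prognostic model.

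The cost is SAP wording and one extra model run. No further data are needed, and sample size and power stay as they are.
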